#### 1.4.2 Definition of secondary endpoints

Secondary outcomes will include the following at both 1 year and 5 years: (Further details and derivations are provided in section 4)

- Spatial Working Memory (measured using Self ordered search test)
- Digital Vigilance (attention measured using the 'digit' span task [12])
- Verbal Short-term memory (measured using the paired associates learning [13])
- Modified version of Informant Questionnaire on Cognitive Decline in the Elderly (IQCODE SF) [14]
- Instrumental Activities of Daily living (IADL) [15]
- Quality of Life (EQ5D) [16]
- 12-Item Short Form Health Survey (SF12) [17]
- Patient Enablement Scale [18]
- Brief Geriatric Depression Scale (GDS) [19, 20]
- Short Warwick Edinburgh Mental Well-Being Scale (SWEMWBS) [21]
- Diagnosis of dementia
- Death
- International Physical Activity Questionnaire (IPAQ) plus strength and balance items [22]
- Dietary behaviour (food frequency questionnaire, with the addition of 2 items about nuts and oils) [23]
- Brain training behaviours

#### 1.4.3 Process measures

- Problematic Experiences of Therapy Scale (PETS) [24]
- Self-efficacy for exercise scale [25]
- mMOS Social Support Survey 8 item [26, 27]
- Social Support for Exercise scale [28]
- Locus of Causation in Exercise [29]
- Technology Acceptance Model Perceived Ease of Use scale [30-32]
- Pedometer use/purchase
- Cognitive performance measures, IQCODE, IADL, EQ5D and FFQ at 2, 3, and 4 years.

## 1.5 Analysis principles

All analyses will be reported according to CONSORT 2010 on planning, implementing and reporting statistical analyses [33] and ICH E9 (R1) addendum on estimands and sensitivity analysis in clinical trials to the guideline on statistical principles for clinical trials [34].

## 2 Design considerations

### 2.1 Description of trial design

There are two parallel trials with the same trial interventions:

- 1) one trial for patients with cognitive decline (lower cognitive score)
- 2) a second trial for patients without signs of cognitive decline (higher cognitive score)

Participants will be randomly allocated to one of three study groups (ratio 1:1:1)

- 1. Usual care
- 2. Access to the Active Brains website
- 3. Access to the Active Brains website with flexible human support from a central support facilitator

## 2.2 Trial power and sample size

## **Cognitive decline trial**

For the primary outcome of cognitive decline at 5 years we assume an alpha of 0.05 and 80% power to detect a standardised effect of 0.15. This requires 698 per group for the MCI subgroup and the same again for the AACD subgroup. Assuming that 60% will be available to provide follow-up within 5 years, that rises to 698\*3/0.6=3490 participants with MCI and the same with AACD per group or 6980 in total.

Although the reduction in cognitive decline as assessed using the Baddeley reasoning test is the primary outcome at one year, the limiting factor in the sample size calculation for those with cognitive impairment is the progression to dementia at 5 years (see outcome definition in section 4.5.9). We assume a 5% annual progression rate to dementia among those who are cognitively impaired. With alpha 0.05 and 80% power, we aim to detect a difference of 5% after 5 years (20% intervention and 25% control) in those diagnosed with dementia. This means we would need 1094 in each of the MCI and AACD groups or a total of 2188. Assuming that 60% will be available to provide follow up in 5 years requires 3647 in each of the 3 study groups or 10940 in total.

## Non-cognitive decline trial

We assume few of those who have no cognitive impairment at baseline will develop dementia. For the primary outcome of cognitive decline we assume an alpha of 0.05 and 90% power to detect a standardised mean difference of 0.1 in the Baddeley. This requires 2103 per group. Assuming that 60% will be available to provide follow-up within 5 years, that rises to 3505 per group or 10,515 in total.

## Therefore:

- In patients with cognitive decline we will recruit a minimum of 3647 patients to each of the three study groups (10,940 total); there will be a mixture of patients with MCI and AACD.
- In patients without cognitive decline we will recruit a minimum of 3505 patients to each of the three study groups (10,515 total).

This means our total sample size across both trials will be a minimum of 21,455 participants in the trials. Since the interventions are identical in both trials we will not only be able to analyse the two trials separately but also as a combined data set.

#### 2.3 Randomisation details

Patients will be randomised online using the study software, which performs simple randomisation and concealment. Once randomised, participants will be informed of their group allocation (they will also be emailed this information). If participants are in one of the treatment arms they will be taken directly to Active Brains where they can begin the intervention. The participants, supporters and study team are unblinded, but the statistician will remain blinded.

## 2.4 Timing of planned analyses

All primary and secondary analyses will take place when all patients have completed one year follow up. Five-year follow-up is contingent on evidence of effectiveness in changing behaviour and improving cognition at 1 year.

## 2.4.1 Interim analyses and early stopping

No interim analyses are planned

## 2.4.2 Stopping rules

No stopping rules planned

## 2.5 Final analysis

All primary and secondary analyses will take place when all patients have completed one year follow up. If there is evidence of effectiveness in changing behaviour and improving cognition at 1 year, analysis will also be undertaken at 5 year follow up.

#### 3 Statistical considerations

## 3.1 Definition of analysis populations

The primary analysis will analyse the two trials (cognitive decline and non cognitive decline) separately. We will then explore as a secondary analysis whether both trial datasets can be combined for modelling, particularly for any pre-planned subgroup analyses.

#### 3.1.1 Intention-to-treat analysis population

The intention to treat (ITT) population includes all randomised patients in the arm to which they were randomised regardless of intervention adherence. All summaries and analysis will be on the ITT population unless otherwise specified.

## 3.2 Analysis software

Analysis will be carried out using Stata version 17 or higher.

## 3.3 Methods for handling data

#### 3.3.1 Withdrawal from trial

All data up until the point of patient withdrawal from the trial will be used in analyses unless the patient withdrew consent and does not wish for the data already collected prior to withdrawal to be used for the trial.

## 3.3.2 Missing data

Multiple imputation with chained equations will be used for the primary outcome and will be implemented in the mice package in Stata. The imputation model will include all variables in the analysis model and auxiliary variables, which predict the outcome or the missingness of the outcome. Predictors of the outcome or its missingness will be ascertained using LASSO regression [35]. Further details are provided in section 4.4. However, we will also include sensitivity analyses using delta-based multiple imputation, to explore the impact of a better or worse outcome for the missing values than those imputed under MAR. We will also present a sensitivity analysis using complete cases only.

#### 3.3.3 Outliers

Outliers will be defined as any data point more than 3 standard deviations from the mean. If outliers are found in regression modelling, then firstly the source data will be checked. If the source data shows that the data is correct, then sensitivity analysis excluding the outliers will be conducted to explore any difference in inferences.

## 3.3.4 Assumption checking and alternative methods

Assumptions for linear regressions will be checked using QQ plots for normality and residual vs fitted value plots for linearity and homoscedasticity. If linear modelling assumptions are not met, the data will be transformed using, e.g., Box Cox transformation and back transformed at values of interest.

#### 3.3.5 Data transformations

No further data transformations will be used.

## 3.4 Definition of key derived variables

Derivations of scores are provided for each endpoint in section 4.

## 3.5 General principles for reporting and analysis

Analyses will in general be reported using a significance level of 5%, corresponding to 95% confidence intervals unless otherwise stated. There will be no adjustment for multiplicity. Each active intervention arm will be compared to usual care. Descriptive statistics will be reported to 1 decimal place as number and percentage for categorical variables, and mean and standard deviation for continuous variables, or median and interquartile range for variables with a skewed distribution. The groups will be labelled Usual Care, Active Brains and Active Brains plus support.

#### 4 Planned analyses and reporting

## 4.1 Disposition of the study population

CONSORT flow diagram (following CONSORT guidelines) which should include:

- Screening data total number screened, reasons for not entering trial)
- Summary of eligibility data to be presented total number assessed for eligibility, breakdown of patients screened against the eligibility criteria
- Recruitment information number consented, recruited/randomised, receiving allowed treatment, withdrawing/lost to follow up at each time point
- Analysis population number included, reasons excluded

#### 4.2 Protocol deviations

A protocol deviation is an unanticipated or unintentional divergence or departure from the expected conduct of a study inconsistent with the protocol, consent documents or other study procedures. Of particular importance are major deviations (violations) which may expose participants to increased risk; compromise the integrity of the entire study or affect participant eligibility. Protocol deviations, as reported on the eCRF page, will be listed with information on treatment group and the type of deviation. Full details of the protocol deviations will also be listed. Failure to engage with the randomised intervention will not be taken as a protocol deviation and neither will use of other websites by participants in the control group.

#### 4.3 Baseline and demographic characteristics

Baseline outcome measures are listed in Table 1 and include:

- Patient socio-demographic measures: age, date of birth, gender, index of multiple deprivation indices; internet experience, education level, work status, ethnicity, height, weight
- Clinical/behavioural measures collected from patient report: Health conditions and medications, family history of dementia, smoking status, alcohol intake, BMI, potential dementia status.

#### 4.4 Primary endpoint

The Baddeley verbal reasoning score at 1 year will be analysed using linear regression, adjusting for baseline Baddeley verbal reasoning score and age, gender, IMD score, number of comorbidities and polypharmacy (yes/no). Adjustment for prognostic covariates, specified a priori, is now commonly recommended in the primary analysis of trial data and can potentially increase power [36, 37]. Assumptions for linear regression will be checked using QQ plots for normality and residual vs fitted value plots for linearity and homoscedasticity. If linear modelling assumptions are not met, the data will be transformed using, e.g., a Box Cox transformation and back transformed at values of interest.

The primary analysis will use multiple imputation with chained equations. The imputation model will include all variables in the analysis model and any baseline covariates predictive of

the Baddeley verbal reasoning score or its missingness. Predictors of missingness will be ascertained using Lasso regression [35]. Potential auxiliary variables will include all baseline variables. A model for outcome that includes randomised group, baseline outcome and all potential auxiliary variables will be fitted using the LASSO with 10-fold cross-validation [38]. The regularization penalty (denoted by  $\lambda$ ) will be chosen such that the cross-validation error was within one SE of the minimum [39]. The auxiliary variables that are included in the fitted model from the LASSO will be included in the imputation model for the outcome, i.e., the LASSO will used to select variables for the imputation model but not to estimate parameters of the imputation model. One hundred imputations will be performed and the imputed estimates will be combined using Rubin's rules. Imputation will be performed separately by randomised group and then combined [40].

All tests will be two-tailed with point estimates and 95% confidence intervals for the treatment effect presented. No formal adjustment for multiple significance testing will be applied. Analyses will be performed using Stata version 17 or above.

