#### 1.4.1 Definition of primary endpoint

The primary outcome is the Baddeley Verbal Reasoning score [10, 11] at 1 year.

The primary outcome at 5 years will be the diagnosis of dementia. The primary definition of dementia diagnosis will be based on diagnosis in the notes. Sensitivity analyses to this definition are provided in section 4.5.9.

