### 4.5.2 Cognitive performance tests

Cognitive performance tests include:

- Spatial Working Memory (measured using Self ordered search test)
- Digital Vigilance (attention measured using the 'digit' span task)
- Verbal Short-term memory (measured using the paired associates learning)

These are continuous scores and will be analysed in the same way as the primary outcome, adjusting for the baseline test score and the same covariates as in the primary analysis.

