## 4.5.10 Diagnosis of dementia

Diagnosis of dementia will be obtained from notes review. This will be analysed using logistic regression, adjusting for the same covariates as in the primary analysis.

The primary definition of dementia will be based on:

1. If there is a notes diagnosis of dementia participants will be classed as having dementia.

As sensitivity analyses, we will use the following methods to ascertain the dementia outcome:

- 2. As recording in notes is suboptimal, consider self-report item "Has a doctor or other medical worker ever said that you have dementia?" (Y/N) this data currently collected in baseline and year 1 and year 5 follow-up online/paper measures.
- 3. Evidence of significant decline in Baddeley (baseline to follow-up) **AND** evidence of functional deterioration (**EITHER**: a) significant change in self-report IQCODE (baseline to follow-up) **OR** b) two self-report questions on difficulty in finance and planning\* (NB the Caerphilly study was based on informant not self-report). Difficulty in finance and planning items collected in year 5 online/paper measures.

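### The 1-year Baddeley model leaves out baseline cognitive tests and education that are already collected: a modest loss of efficiency, not a bias or a power shortfall

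*SAP*

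**What the plan says.** **1-year primary outcome.** SAP 4.4 specifies linear regression "adjusting for baseline Baddeley verbal reasoning score and age, gender, IMD score, number of comorbidities and polypharmacy (yes/no"). It gives its reason for adjusting: "Adjustment for prognostic covariates, specified a priori, is now commonly recommended in the primary analysis of trial data and can potentially increase power". It gives no reason for choosing these covariates over others, and no R-squared or correlation.

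**What else is measured at baseline.** SAP 4.3 lists, among the baseline variables, "internet experience, education level, work status, ethnicity, height, weight". The baseline columns of SAP Table 1 and protocol Table 2 also hold spatial working memory, digit span, paired associates learning, self-report IQCODE and IADL. SAP 4.5.2 confirms that the three other cognitive tests have a baseline score, since they are analysed "adjusting for the baseline test score and the same covariates as in the primary analysis".

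**Where those variables may be used.** SAP 4.4 makes them candidates for the imputation model: "Potential auxiliary variables will include all baseline variables". LASSO then selects among them.

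**5-year dementia outcome.** SAP 1.4.1 states: "The primary outcome at 5 years will be the diagnosis of dementia". For its model, SAP 4.5.10 says: "This will be analysed using logistic regression, adjusting for the same covariates as in the primary analysis".

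**The concern.** Other cognitive tests taken at the same visit, and education, are natural candidates to predict a later verbal reasoning score. A model that adjusts for deprivation and polypharmacy but not for these seems to fall short of the SAP's own reason for adjusting. If they carry information beyond baseline Baddeley and age, leaving them out makes the confidence interval for each intervention effect wider than it needs to be. That would be felt most in the treatment-by-MCI interaction (SAP 4.4.1), which is less precise than the main comparison.

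There is also a gap in wording for dementia. Elsewhere in SAP 4.5 the baseline score of the outcome is named separately from the shared covariates. It is therefore unclear whether the covariates carried over to the dementia model include baseline Baddeley.

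**Working it through.** **1. Do the planned sample sizes rely on adjustment?** Inputs are from SAP 2.2 and the protocol's sample size section; tests are two-sided (SAP 4.4).

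- Decline trial, Baddeley: n = 2(1.960 + 0.842)² / 0.15² ≈ 698 per arm and subgroup, as stated. Totals: 698 × 6 / 0.7 = 5,983 and 698 × 6 / 0.6 = 6,980, as stated.
- Non-decline trial, Baddeley: n = 2(1.960 + 1.282)² / 0.1² ≈ 2,102, against 2,103 stated. Totals: 2,103 × 3 / 0.7 = 9,013 and 2,103 × 3 / 0.6 = 10,515, as stated.
- Dementia, 25% v 20%, 80% power, pooled variance, no continuity correction: 1,094 per arm and subgroup, as stated. Total: 2,188 × 3 / 0.6 = 10,940, as stated.

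None of these uses covariate adjustment, so the omission cannot make the plan underpowered on its own terms. With 2,188 evaluable per arm in the decline trial, unadjusted power is 99.9% for a standardised difference of 0.15 and 97.7% for 25% v 20%. In the non-decline trial, 3,505 × 0.7 ≈ 2,453 per arm gives about 94% for 0.1.

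**2. Gross gain in the linear model.** Let p be the partial R-squared of the added variables given those already in the model. The standard error is multiplied by √(1 − p). The documents do not give p, so 0.01 to 0.15 is assumed. The gross reduction is 0.5% at p = 0.01, 2.5% at 0.05, 5.1% at 0.10 and 7.8% at 0.15.

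**3. Net gain after imputation.** Let f be the fraction observed, 0.7 at 1 year (protocol). Take outcomes as missing completely at random and the added variables as selected into the imputation model. In units of the residual variance under the current covariates, the variance of the effect estimate is proportional to:

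- no use of the variables: 1/f
- imputation auxiliaries only (current plan): (1 − p)/f + p
- in the analysis model: (1 − p)/f

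The full gain is p/f. The auxiliary route recovers p/f − p, a share of 1 − f = 30%. What remains is the ratio of the last two lines:

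| p | current plan | added to model | SE ratio | net SE reduction |
|---|---|---|---|---|
| 0.01 | 1.4243 | 1.4143 | 0.996 | 0.4% |
| 0.05 | 1.4071 | 1.3571 | 0.982 | 1.8% |
| 0.10 | 1.3857 | 1.2857 | 0.963 | 3.7% |
| 0.15 | 1.3643 | 1.2143 | 0.943 | 5.7% |

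A simulation with 500 per arm, 30% missing, imputation by arm, 20 imputations and 1,500 runs gave 1.9% at p = 0.05 and 4.2% at p = 0.15. The first agrees with the formula; the second is somewhat smaller.

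**4. Dementia (logistic model).** Simulation used 1,094 per arm, 25% v 20%, 3,000 runs per setting, and existing covariates with an assumed log odds of 0.7 per SD. The added predictors had assumed log odds of 0.3 to 1.1 per SD.

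- AUC rose from 0.68 to 0.70 in the weakest case and from 0.66 to 0.79 in the strongest.
- Power rose from 82.7% to 83.2% and from 82.9% to 88.0%.
- The standard error of the log odds ratio did not fall. It rose from 0.107 to 0.108 and from 0.106 to 0.116, while the log odds ratio moved away from zero (−0.311 to −0.316, and −0.304 to −0.363).

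**The case against.** The strongest reply is that the SAP pre-specifies a short list, cites guidance for it, and already goes beyond the protocol, which asks only for adjustment for baseline values. The two covariates that might be expected to matter most, baseline Baddeley and age, are in the model. The omitted variables are not ignored either, since imputation can use them. Nothing is biased or contradictory, and power at full recruitment is ample.

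Most of this stands. It makes the point an efficiency improvement rather than a correction. The remaining gain rests on a partial R-squared that nobody can read from the documents: if the other tests relate to later reasoning only through baseline reasoning, the gain is zero. It also stands that more covariates mean more missing baseline values. SAP 3.3.2 and 4.4 describe imputation of the outcome and state no rule for missing covariates. For dementia, imputation appears only among the sensitivity analyses in 4.5.10, so added covariates could drop participants from the main model.

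What does not stand is that imputation makes the change redundant. At 30% missing it recovers about 30% of the possible variance gain and leaves about 70%.

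**Conclusion.** The point holds as a modest, nearly free gain for the 1-year linear model. Adding the three baseline tests and education would cut the standard error by about 0.4% to 5.7%, assuming a partial R-squared of 0.01 to 0.15 and 30% missing outcomes. It helps confidence-interval width and the MCI interaction analysis rather than the main test. That these measures precede randomisation is a fair reading of the baseline columns and the screening procedure, though not stated for each one.

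Four stronger readings are tempting and not supported:

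- *That precision is lost on dementia too.* In a logistic model, further predictors raise the standard error of the log odds ratio and change the conditional odds ratio being estimated. The gain is some power.
- *That dementia power would climb from about 80% into the mid-80s.* That takes 1,094 per arm, the figure for one subgroup. SAP 3.1 analyses each trial as a whole, with 2,188 evaluable per arm and 97.7% power unadjusted.
- *That selecting the decline trial on baseline Baddeley enlarges the gain.* Selection does weaken that covariate. Under a normal model, however, the partial R-squared of the other tests given baseline Baddeley does not change when the sample is truncated on it.
- *That the plan's own view of dementia makes memory and IQCODE indispensable.* The protocol's background says that people outside the MCI definition are at similar risk. A "significant change in self-report IQCODE (baseline to follow-up" enters only a sensitivity definition; the primary definition is a diagnosis in the notes.

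**What to change.** Before unblinded data are seen:

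1. **SAP 4.4.** Add baseline spatial working memory, digit span, paired associates learning and education level to the linear model in both trials. Report the current covariate set as a sensitivity analysis.
2. **Missing baseline values.** State a rule, for example imputing them so that no randomised participant is dropped.
3. **SAP 4.5.10.** State whether the dementia model includes baseline Baddeley. Adding baseline paired associates, IQCODE, IADL or education is optional. If it is done, report a standardised risk difference beside the conditional odds ratio and apply the same missing-baseline rule.

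The cost is SAP wording, a few degrees of freedom and the handling of missing baseline scores. No new data are needed.
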